## 1.5.4 Visits windows

*Visit-windows* will be used for the data that is summarized by visit; they are based on the study evaluation schedule and comprise a set of days around the nominal visit day. For any assessment, there are protocol defined scheduled visits around which visit windows were created to cover the complete range of days within the study. The visit windows are shown in Table 1-5. In this table, the days are counted since the first dose of study treatment in extension (study days in extension) for safety assessments and the days are counted since the date of randomization in extension for efficacy assessments. These visit windows apply to measurements taken at every visit. For assessments collected less often different visit windows will be applied as detailed below.

When visit windows are used, all visits will be re-aligned, i.e., they will be mapped into one of the visit windows. E.g., if the *Week 56* visit of a subject is delayed and occurs on Day 46 instead of on Day 29, say, it will be re-aligned to visit window *Week 60*. In the case of major deviations from the visit schedule, or due to unscheduled visits, several assessments of a subject may fall in a particular visit window (either scheduled or unscheduled). Statistical approaches to handle multiple assessments in a given visit window are specified below in section 1.5.5.

Of note, subjects are allowed to have gaps in visits.

The analysis visit will be used for listing of visit and period. If a visit falls after the last visit window (after Day 1527 in the example below) it is not assigned to analysis visit and will be listed under label "After Week 268".

For the open label period, only the scheduled site visits are included in the table below.

## Table 1-5Visit windows for scheduled visits relative to Week 52

Novartis			
RAP Module 3			

Analysis Visit	Week (relative to baseline of core)	Scheduled Day	Visit Window
Week 52/baseline	52	1	Up to Day 1*
Week 56	56	29	Day 2-43
Week 60	60	57	Day 44-71
Week 64	64	85	Day 72-99
Week 68	68	113	Day 100-127
Week 72	72	141	Day 128-155
Week 76	76	169	Day 156-183
Week 80	80	197	Day 184-211
Week 84	84	225	Day 212-239
Week 88	88	253	Day 240-267
Week 92	92	281	Day 268-295
Week 96	96	309	Day 296-323
Week 100	100	337	Day 324-351
Week 104	104	365	Day 352-379
Week 108	108	393	Day 380-407
Week 112	112	421	Day 408-435
Week 116	116	449	Day 436-463
Week 120	120	477	Day 464-491
Week 124	124	505	Day 492-519
Week 128	128	533	Day 520-547
Week 132	132	561	Day 548-575
Week 136	136	589	Day 576-603
Week 140	140	617	Day 604-631
Week 144	144	645	Day 632-659
Week 148	148	673	Day 660-687
Week 152	152	701	Day 688-715
Week 156	156	729	Day 716-743
Week 168	168	813	Day 744-855
Week 180	180	897	Day 856-939
Week 192	192	981	Day 940-1023
Week 208	208	1093	Day 1024-1149
Week 220	220	1177	Day 1150-1219
Week 232	232	1261	Day 1220-1303
Week 244	244	1345	Day 1304-1387
Week 260	260	1457	Day 1388-1471
Week 264	264	1485	Day 1472-1499
Week 268	268	1513	Day 1500-1527
3 WK after last study drug admin.**			Week 264 visit

Novartis	Confidential	Page 21
RAP Module 3	9-Apr-2018 (1:15)	Secukinumab / AIN457A2302E1

12 WK after last study		Week 268 visit
drug admin.**		

\* Baseline measurement before the first drug administration for safety assessments and before the randomization for efficacy assessments. The days are counted since the first dose of study treatment in extension for safety assessments, and the days are counted since the date of randomization in extension for efficacy assessments.

\*\* 8/12 WK after last study drug administration will be used for re-bound analysis.

For parameters which are not collected at every visit (e.g. DLQI, EQ-5D, HAQ-DI), visit windows defined in Table 1-5 will be combined. For example, if a parameter is measured at Week 64 and Week 76 only, Week 64 visit window will extend from Day 2 to Day 99 (combining Week 56 to Week 64 visit windows), Week 76 will extend from Day 100 to Day 183 (combining Week 68 to Week 76). If more than one assessment falls into the interval, the rules defined in section 1.5.5 below are applied.

Assessments from treatment period will not be considered for RW period. Assessments from RW period will not be considered for treatment period. Assessments from RW and treatment period may be considered for follow-up period.

Assessments from RW/treatment period will not be considered for open label period. Assessments from open label period will not be considered for RW/treatment period.

The 'by visit' safety summaries for the 'whole treatment period' will be reported as per the analysis visits relative to Week 52 as defined in Table 1-5.

Of note, for subjects who discontinue in RW period, i.e. not moving into treatment period, efficacy measurements taken in follow-up period would still be considered for RW period as specified in Section 1.9.4.1.

## 1.5.4.1 Visits windows for subjects with relapse

Visit windows for subjects who relapsed (either in PASI 75 responders or partial responders) will be defined analogously to general visit windows as defined in section 1.5.4, but the days are counted since the date of relapse for efficacy assessments including PASI response and IGA 0/1 response. The visit windows are shown in Table 1-6.

#### Table 1-6 Visit windows for subjects re-treated after relapse

Analysis Visit	Week after relapse	Day	Visit Window
Week 0	0	1	Up to Day1
Week 1 after relapse 	1	8	day 2-11
Week 2 after relapse 	2	15	day 12-18
Week 3 after relapse 	3	22	day 19-25
Week 4 after relapse	4	29	day 26-43
Week 8 after relapse	8	57	day 44-71
Week 12 after relapse	12	85	day 72-99
Week 16 after relapse	16	113	day 100-127
Week 20 after relapse	20	141	day 128-155
Week 24 after relapse	24	169	day 156-183
Week 28 after relapse	28	197	day 184-211
Week 32 after relapse	32	225	day 212-239
Week 36 after relapse	36	253	day 240-267
Week 40 after relapse	40	281	day 268-295
Week 44 after relapse	44	309	day 296-323
Week 48 after relapse	48	337	day 324-351
Week 52 after relapse	52	365	day 352-379
Week 56 after relapse	56	393	day 380-407
Week 60 after relapse	60	421	day 408-435
Week 64 after relapse	64	449	day 436-463
Week 68 after relapse	68	477	day 464-491
Week 72 after relapse	72	505	day 492-519
Week 76 after relapse	76	533	day 520-547
Week 80 after relapse	80	561	day 548-575
Week 84 after relapse	84	589	day 576-603
Week 88 after relapse	88	617	day 604-631
Week 92 after relapse	92	645	day 632-659
Week 96 after relapse	96	673	day 660-687
Week 100 after relapse	100	701	day 688-715
Week 104 after relapse	104	729	day 716-743
Week 108 after relapse	108	757	day 744-771

 $^{1}$  = Applicable for subjects with relapse in RW period only.

Novartis	Confidential	Page 23
RAP Module 3	9-Apr-2018 (1:15)	Secukinumab / AIN457A2302E1

#### 1.5.5 Multiple assessments within visit windows

When there are *multiple assessments* in a particular visit window, the following rules are applied to select one value "representing" the subject in summary statistics in a visit window (See Table 1-5 & Table 1-6).

For subjects with relapse switching from PBO to AIN XX, the assessments taken while subject receiving placebo will be considered in RW period and the assessments taken while secukinumab will be considered in treatment period.

For baseline assessment definition see Section 1.5.3. For post-baseline visit windows the following applies (unless otherwise specified):

- for *quantitative variables*, the *closest* to the actual visit is chosen (if two assessments have the same distance, then the earlier one will be chosen);
- for *qualitative variables*, the *worst* record is selected. It is noted that in the analyses performed, *worst* case is always well defined (e.g., for urine protein values "+" and "++", the worst case is defined as "++"),
- in case qualitative variables are based on quantitative variables, e.g. PASI 75 response, the visit will be assigned to the quantitative variable, and this visit will be used for the derived qualitative variable.

	•	
Timing of measurement	Type of data	Rule
Baseline	All data	See Section 1.5.3
Post-baseline efficacy	All data except DLQI, EQ-5D and health assessment	The measurement closest to the target day will be used. In the event two measurements are taken equally apart (e.g., 1 day before target date and 1 day after), the earlier one will be used
Post-baseline efficacy	DLQI, EQ-5D and health assessment	The measurement closest to the target day will be used. In the event two measurements are taken equally apart the earlier one will be used. If two measurements have been taken on the same day, select the worst.

Table 1-7Rules for selecting values for analysis

Timing of measurement	Type of data	Rule
Post-baseline safety	Summary visit information (e.g. lab, ECG, etc.)	The non-missing measurement closest to the target day will be used. In the event two measurements are taken equally apart (e.g., 1 day before target date and 1 day after), the earlier one will be used. If two measurements are taken on the same day then select the first one (using the time). If two measurements are taken
		on the same date/time then use the first visit number (assuming this is the planned visit).
Post-baseline safety	Notable abnormalities (e.g., vital signs, ECG), CTCAE grades	The most extreme measurement in the window will be used. Note this means a subject can have a notably high and notably low measurement within a window (analysis period).

## 1.5.6 Day of last dose of randomized study treatment

[figure not shown]
The date of last dose will be collected in the CRF. The subject's exposure will not be calculated using last dose. It will be calculated considering the last visit in RW period for PASI 75 responders and last visit in treatment period for partial responders as well as subjects re-treated after relapse. If a subject in RW period discontinued early, then the last visit during the RW period is considered. If a subject in treatment period discontinued early, then the last visit during the treatment period is considered.

# 1.6 Subject disposition, background and demographic characteristics

#### 1.6.1 Subject disposition

The number and percentage of subjects in the randomized set who completed study periods), and who discontinued the study prematurely (including the reason for discontinuation) will be presented by study period for each treatment group and all subjects.

Since the study design is very complicated, the disposition will be provided based on below flow chart.

All 150 mg in red; All 300 mg in blue; Placebo in green

For each protocol deviation, the number and percentage of subjects for whom the deviation applies will be tabulated.

#### 1.6.2 Background and demographic characteristics

The following common background and demographic variables will be analyzed for assessing the baseline comparability:

#### Continuous variables:

- Age at extension baseline (which is derived from date of birth and the screening assessment date)
- Height (at core study baseline and extension baseline)
- Weight (at core study baseline and extension baseline)
- Body mass index (BMI) (at core study baseline and extension baseline)

#### **Categorical variables:**

- Age categories (<65 years, 65 years and older, 75 years and older) at extension baseline
- o Gender
- o Race
- o Ethnicity
- Smoking status at core baseline

Psoriasis specific baseline characteristics and history of disease will be summarized as well: baseline PASI(at core study baseline and extension baseline), extension baseline PASI 75 responders, extension baseline PASI partial responders, baseline IGA mod 2011 score (at least mild, moderate, severe) (at core study baseline and extension baseline), types of previous psoriasis therapies at core study baseline , previous exposure to biologic systemic psoriasis

Novartis	Confidential	Page 26
RAP Module 3	9-Apr-2018 (1:15)	Secukinumab / AIN457A2302E1

therapy, previous exposure to systemic psoriasis therapy, previous exposure to non-biologic systemic psoriasis therapy, previous failure to biologic systemic psoriasis therapy, previous failure to non-biologic systemic psoriasis therapy.

Body Mass Index (BMI) will be calculated using the following formula:

BMI = (body weight in kilograms) / (height in meters)

For BMI, height and body weight used is the last value prior to randomization at core study baseline and extension baseline. If there is no weight recorded prior to taking of study treatment, BMI will be missing.

Unless otherwise specified, summary statistics will be presented for continuous variables for each treatment group and for all subjects (total) in the randomized set. The number and percentage of subjects in each category will be presented for categorical variables for each treatment group and all subjects (total) in the randomized set.

#### 1.6.3 Medical history

Any significant prior or active medical condition at the time of signing informed consent will be coded using the MedDRA dictionary. These medical conditions will be summarized by primary system organ class and preferred term. Concurrent or medical history of disease of interest will be summarized by categories and treatment group.

All the medical history information will be retrieved from the core studies.

## 1.7 Study medication

The analysis of study treatment data will be based on the safety set.

In case it cannot be identified from the data collected or assumed from the planned treatment whether an injection contained placebo or secukinumab, it will be assumed that the syringe contained secukinumab. This applies for example to the 150 mg secukinumab treatment group (in which subjects should receive both an active and a placebo injection) if only one injection is given. If the medication pack number is not available, it will be assumed that the secukinumab injection was applied. If this scenario occurs for subjects in the 300 mg treatment group or in the placebo treatment group, respectively, when subjects should receive two identical injections, it will be assumed that they received secukinumab or placebo, respectively, as planned.

The duration of exposure to study treatment in the extension will be summarized by treatment group. In addition, the number of subjects with exposure of at least certain time thresholds will be displayed. The following categories will be presented: "any exposure", " $\geq$ 4 weeks", " $\geq$ 8 weeks", " $\geq$ 12 weeks", and so on with an increase of time threshold by 4 weeks until there are some subjects in the category or the last category " $\geq$ 256 weeks" is presented.

Duration of exposure will be defined and summarized as follows:

Duration of exposure is defined as the time from first dose of study medication in the extension to the last dose plus 84 days or last visit whichever occurs earlier. i.e., for subjects who discontinued or have their last visit earlier than 84 days, the end of study treatment exposure will be the date of the last study visit.

Novartis	Confidential	Page 27
RAP Module 3	9-Apr-2018 (1:15)	Secukinumab / AIN457A2302E1

Duration of exposure (days) = min ('last study visit' date, last dose date +84) – first dose date +1

Duration of exposure (years) = duration of exposure (days) / 365.25

Duration of exposure (100-patient years) = duration of exposure (years) / 100

The analyses of duration of exposure described above will be done for the entire study treatment period.

## 1.8 Concomitant medication

Medications will be identified using the Novartis Drug and Therapy Dictionary (NovDTD) including Anatomical Therapeutic Chemical (ATC) code. Prior and concomitant treatments will be summarized by treatment group for the safety set.

Prior and concomitant medications will be summarized by treatment group in separate tables. Medications will be presented in alphabetical order, by ATC codes and grouped by *anatomical main group* (the 1st level of the ATC codes). Tables will also show the overall number and percentage of subjects receiving at least one drug of a particular ATC code and at least one drug in a particular anatomical main group.

Background therapies such as MTX or other DMARDs might be excluded from concomitant medications, if appropriate for the indication.

Prior medications are defined as drugs taken and stopped prior to first dose of study treatment in core studies. Any medication given at least once between the day of first dose of randomized study treatment and the last day of study visit will be a **concomitant** medication, including those which were started pre-baseline and continued into the RW period/ treatment period.

Indication specific summaries of prior and/or concomitant medication might be presented as well.

For psoriasis this will be done for:

- the categories presented in Table 1-8, but as well for topical, phototherapy and photochemotherapy (yes/no)
- ongoing use of emollients

In addition, medical procedures and significant non-drug therapies as coded in MedDRA will be summarized.

Prior medications will not be re-summarized for extension. They have been summarized in core studies.

Prior or concomitant medication will be identified based on recorded or imputed start and end dates of medication taken. Further rules will be given in PDS.

#### Table 1-8Subgroups based on the previous psoriasis therapy

Level 1 description	Level 1 outcome	Level 2 description	Level 2 outcome	Level 3 description	Level 3 outcome	Level 4 description	Level 4 outcome
previous therapy	yes/no						
systemic	No						
	Yes	number	1				
			2				
			>=3				
		failure*	No				
			Yes				
biologic	No						
	Yes	failure*	No				
			Yes				
		type of previou	s biologic				
	anti-p40	anti-p40	No				
		Yes	failure*	failure* no			
					yes		
		anti-TNF	No				
			Yes	failure*	no		
					yes	lack of primary	no
					efficacy lack of secondary efficacy	efficacy	yes
						lack of secondary	no
						efficacy	yes
						lack of primary or	no
						secondary efficacy	yes
						lack of tolerability	no
							yes
non-biologic	No						
systemic	Yes	failure*	No				
			Yes				
		failure* to at	No				
		least 2	Yes				

Only selected subgroups will be used for reporting

\*: at least one therapy with lack of primary efficacy or lack of secondary efficacy or lack of tolerability

## 1.9 Efficacy evaluation

#### 1.9.1 Variables

Table 1-9 lists the all primary, secondary and exploratory variables for this study. Only part of the variables will be included in the final analysis. The key secondary variables will be re-run for patients who randomized to RW period or for retreated patents after relapse.

#### Table 1-9Primary, secondary and exploratory variables

Variable	Туре	Analysis
cumulative rate of subjects who lost PASI 75 response up to Week 68 (compared to placebo) after 52 weeks of treatment	Primary	No analysis
PASI 50/75/90/100 and IGA mod 2011 0 or 1 response over time	Secondary	Final analysis Re-run during RW period and for relapse patients after re-treated
Loss of PASI 75 response over time after 52 weeks of treatment	Secondary	Re-run during RW period
Loss of IGA 0 or 1 response over time after 52 weeks of treatment	Secondary	Re-run for PASI 75 responders during RW period
PASI score over time	Secondary	Final analysis
IGA mod 2011 score over time	Secondary	Final analysis
Relapse	Secondary	Final analysis
Rebound	Secondary	Final analysis
Time to PASI 75 response	Secondary	No analysis
Time to IGA 0 or 1 response	Secondary	No analysis
EQ-5D	Secondary	Final analysis
DLQI	Secondary	Final analysis Re-run during RW period
DLQI 0 or 1 achievement	Secondary	Final analysis Re-run during RW period
HAQ-DI score over time 	Exploratory	Final analysis
HAQ-DI response over time 	Exploratory	Final analysis

only for subjects with psoriatic arthritis (PsA) at baseline of core study

#### 1.9.1.1 Definition of PASI and related variables

The total BSA affected by plaque-type psoriasis was estimated from the percentages of areas affected, including head, trunk, upper limbs and lower limbs (see below for PASI assessment). The following calculations were done: each reported percentage was multiplied by its respective body region corresponding factor (head = 0.1, trunk = 0.3, upper limbs = 0.2, lower limbs = 0.4). The resulting 4 percentages will be added up to estimate the total BSA affected by plaque-type psoriasis. The PASI scoring system is further described in Table 1-12.

A PASI score (Fredriksson and Pettersson 1978, Weisman et al 2003, Gottlieb et al 2005) was derived as indicated in Table 1-12. The head, trunk, upper limbs and lower limbs are assessed separately for erythema, thickening (plaque elevation, induration), and scaling (desquamation). The average degree of severity of each sign in each of the four body regions is assigned a score of 0-4. The area covered by lesions on each body region is estimated as a percentage of the total area of that particular body region. Further practical details help the assessment:

Novartis	Confidential	Page 30
RAP Module 3	9-Apr-2018 (1:15)	Secukinumab / AIN457A2302E1

- 1. The neck is assessed as part of the head.
- 2. The axillae and groin are assessed as part of the trunk.
- 3. The buttocks are assessed as part of the lower limbs.
- 4. When scoring the severity of erythema, scales should not be removed.

Because the head and neck, upper limbs, trunk and lower limbs correspond to approximately 10%, 20%, 30% and 40% of the body surface area, respectively, the PASI score was calculated using the formula:

 $PASI = 0.1 (E_h + I_h + D_h)A_h + 0.2 (E_u + I_u + D_u)A_u + 0.3 (E_t + I_t + D_t)A_t + 0.4 (E_l + I_l + D_l)A_l$ 

where E, I, D, and A denote erythema, induration, desquamation, and area, respectively, and h, u, t, and l denote head, upper extremities, trunk, and lower extremities, respectively (see Table 1-10).

PASI scores can range from a lower value of 0, corresponding to no signs of psoriasis, up to a theoretic maximum of 72.0.

The investigator was only responsible for collecting the components or scoring signs and total regional area. PASI calculations were done via the PASI Score eCRF.

The PASI scores calculated via the PASI Score eCRF will be used in the analysis and for derivation of PASI response values, relapse and rebound (see below).

It should be noted that the true area percentage values were rounded in the eCRF calculations up to the closest integer value. For example, the true area of 0.45% was rounded to 0% (giving area score of 0), and the true area of 0.5% was rounded to 1% (giving area score of 1).

In order to investigate the effect of rounding the true area percentage values on the PASI scores, an additional calculation of PASI scores without rounding the true area percentage values will be done. The area affected by psoriasis within each anatomic area is estimated as a percentage and assigned a numeric value (area score) according to degree of involvement as follows: no involvement = 0; >0% to <10% = 1; 10% to <30% = 2; 30% to <50% = 3; 50% to <70% = 4; 70% to <90% = 5; and 90% to 100% = 6. The PASI score will be calculated using the formula above. The PASI score calculated in this way will be referred to as the PASI score without rounding the true area percentage values.

	1-2 The FASI Scoring System			
Body region	Erythema (E)	Thickening (plaque elevation, induration, l)	Scaling (desquamation, D)	Area score (based on true area %, A)*
Head (H) †	0=none 1=slight 2=moderate 3=severe 4=very severe	0=none 1=slight 2=moderate 3=severe 4=very severe	0=none 1=slight 2=moderate 3=severe 4=very severe	0 = 0% 1 = 1-9% 2 = 10-29% 3 = 30-49% 4 = 50-69% 5 = 70-89% 6 = 90-100%
Trunk (T)‡	0=none 1=slight 2=moderate 3=severe 4=very severe	0=none 1=slight 2=moderate 3=severe 4=very severe	0=none 1=slight 2=moderate 3=severe 4=very severe	0 = 0% 1 = 1-9% 2 = 10-29% 3 = 30-49% 4 = 50-69% 5 = 70-89% 6 = 90-100%
Upper limbs (U)	0=none 1=slight 2=moderate 3=severe 4=very severe	0=none 1=slight 2=moderate 3=severe 4=very severe	0=none 1=slight 2=moderate 3=severe 4=very severe	0 = 0% 1 = 1-9% 2 = 10-29% 3 = 30-49% 4 = 50-69% 5 = 70-89% 6 = 90-100%
Lower limbs (L)§	0=none 1=slight 2=moderate 3=severe 4=very severe	0=none 1=slight 2=moderate 3=severe 4=very severe	0=none 1=slight 2=moderate 3=severe 4=very severe	0 = 0% 1 = 1-9% 2 = 10-29% 3 = 30-49% 4 = 50-69% 5 = 70-89% 6 = 90-100%

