#### Table 1-2 The PASI scoring system

\* Percentage (not score) of body region (not whole body) affected will be entered in the eCRF

+ Neck is assessed as part of the Head (H) body region.

‡ Axillae and groin are assessed as part of the Trunk (T) body region.

§ Buttocks are assessed as part of the Lower limbs (L) body region.

The following definitions are possible efficacy evaluations that can be used in clinical trials in psoriasis (CHMP/EWP/2454/02, 2004):

- **PASI non response:** subjects achieving <50% improvement (reduction) in PASI score compared to baseline are defined as PASI non responders
- **Partial response**: subjects achieving ≥ 50% improvement (reduction) in PASI score but less than 75% compared to baseline are defined as partial responders
- **PASI 50 response**: subjects achieving ≥ 50% improvement (reduction) in PASI score compared to baseline are defined as PASI 50 responders
- **PASI 75 response**: subjects achieving ≥ 75% improvement (reduction) in PASI score compared to baseline are defined as PASI 75 responders

Novartis	Confidential	Page 32
RAP Module 3	9-Apr-2018 (1:15)	Secukinumab / AIN457A2302E1

- **PASI 90 response**: subjects achieving ≥ 90% improvement (reduction) in PASI score compared to baseline are defined as PASI 90 responders
- **PASI 100 response**: complete clearing of psoriasis (PASI=0)
- **Relapse**: when the achieved maximal PASI improvement from baseline PASI in core is reduced by >50%
- **Rebound-like event**: defined as increase of PASI of more than 25% from baseline value or occurrence of new pustular, new erythrodermic or more inflammatory psoriasis **after** stopping therapy
- Rebound: defined as rebound like event occurring within 8 weeks of stopping therapy

The analysis of rebound will be done for the follow-up period.

The number and percentage of subjects experiencing rebound and rebound like events will be presented by treatment group as follows:

- For rebound, all assessments done up to 8 weeks will be summarized.
- Similarly for rebound like events, all assessments done up to 12weeks will be summarized.
  - 1. Rebound up to 8 weeks: For this time-point the worst outcome (i.e. rebound like event=yes) prior to this cut-off is considered (e.g. if a subject had >25% PASI increase at Week 260, but not at Week 264 the subject would be considered as rebounder for this "up to 8 week timepoint").

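### PASI 100 is derived from an eCRF score that sets regional areas below 0.5% to zero, so some subjects with scored lesions count as completely clear, and the SAP assigns no response output to its planned unrounded score

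*SAP*

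**What the plan says.** All of the following is in SAP section 1.9.1.1 unless noted.

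- Source of the responses: "The PASI scores calculated via the PASI Score eCRF will be used in the analysis and for derivation of PASI response values".
- Meaning of the lowest score: the PASI scale starts at "a lower value of 0, corresponding to no signs of psoriasis".
- PASI 100, in the list of response definitions: "complete clearing of psoriasis (PASI=0".
- Rounding: area percentages were "rounded in the eCRF calculations up to the closest integer value". Two examples follow. The first is "the true area of 0.45% was rounded to 0% (giving area score of 0". In the second, an area of 0.5% becomes 1% and scores 1.
- Planned check: "an additional calculation of PASI scores without rounding the true area percentage values will be done". Its area rule gives 0 only for no involvement, and 1 for any area above 0% and below 10%. Its stated purpose is to see how rounding affects PASI scores.
- Use of PASI 100: section 1.9.6 tabulates it by visit. In the randomized withdrawal (RW) period it also compares each dose with placebo at each visit, by a stratified Cochran-Mantel-Haenszel test and logistic regression.

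The variable list (Table 1-9), the overview of efficacy methods (cited in the text as Table 1-13) and section 1.9.6 name no response variable based on the unrounded score.

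Protocol Table 6-3 bases the area score on the true area percentage. It lists whole-number bands, 0 for 0% and 1 for 1-9%, and does not mention rounding. SAP section 1.1.1, on changes from the protocol's methods, does not mention rounding either.

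**The concern.** A PASI of 0 is presented as absence of psoriasis, and PASI 100 as full clearance. The score that decides it can be 0 when the investigator has recorded both an affected area and signs of disease. The SAP's alternative rule would not classify that subject as PASI 100, so one record can give two answers within one section.

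At stake is what the reported PASI 100 rates mean. PASI 100 is one of four PASI response levels shown at every visit, and it will be read as the share of subjects with no psoriasis. The unrounded score that would show the size of the discrepancy is planned, but as written it stops at the score and does not reach the response rates.

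**Working it through.** **Inputs (SAP 1.9.1.1).** Regional weights: head 0.1, upper limbs 0.2, trunk 0.3, lower limbs 0.4. In each region E, I and D are scored 0-4. PASI is the sum over regions of weight × (E+I+D) × area score. The baseline PASI of 20 used for percentages below is my assumption.

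**Step 1: reproduce the SAP's two examples.** Rounding to the nearest integer with halves going up, floor(area + 0.5), gives:
- 0.45%: floor(0.95) = 0, area score 0.
- 0.5%: floor(1.0) = 1, area score 1.

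Both match. Always rounding up would turn 0.45% into 1% and contradict the first example, so nearest-integer rounding is what the examples describe, despite the word "up" in the rule.

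**Step 2: find where the two area rules differ.**

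| True area | eCRF area score minus unrounded area score |
|---|---|
| above 0% and below 0.5% | −1 |
| 9.5 to <10%, 29.5 to <30%, 49.5 to <50%, 69.5 to <70%, 89.5 to <90% | +1 |
| all other areas | 0 |

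Only the first row bears on PASI 100. There the eCRF score is the lower one. In the +1 bands both scores are above 0 whenever signs are scored. Rounding can therefore add PASI 100 responders and cannot remove any.

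**Step 3: apply both rules to single records.**

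| Record | eCRF PASI | Unrounded PASI | Unrounded improvement from 20 |
|---|---|---|---|
| Lower limbs 0.4%, E=I=D=1, rest clear | 0.4×3×0 = 0 | 0.4×3×1 = 1.2 | 1 − 1.2/20 = 94.0% |
| Upper limbs 0.4%, E+I+D=2, rest clear | 0.2×2×0 = 0 | 0.2×2×1 = 0.4 | 1 − 0.4/20 = 98.0% |
| All four regions 0.45%, E+I+D=3 in each | 0 | (0.1+0.2+0.3+0.4)×3×1 = 3.0 | 1 − 3/20 = 85.0% |

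All three are PASI 100 on the eCRF score and not on the unrounded score. In the third, the affected body surface is 0.45%.

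**Step 4: test the condition.** Take the third record and set the head to 0.5%. The eCRF PASI becomes 0.1×3×1 = 0.3, and the subject is no longer PASI 100. Every region with scored signs must be below 0.5%; one small region is not enough.

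**Step 5: check the other response levels.** Trunk 9.6% with E=I=D=2, rest clear: eCRF 0.3×6×2 = 3.6 (82% improvement from 20), unrounded 0.3×6×1 = 1.8 (91%). This is not a PASI 100 case, and here rounding removes a PASI 90 response. At the other thresholds the shift can go either way.

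**The case against.** The strongest reply has five parts.

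1. **The SAP discloses the rounding and plans a check.** This stands: a reader might infer that the sponsor overlooked the problem, and the text shows otherwise. The check as described, however, concerns scores and not response rates.
2. **Output details sit in documents not available here.** The SAP refers to an efficacy MAP, RAP Module 8 and a PDS. This also stands in part. Silence in the SAP does not prove that no unrounded response table exists, only that the SAP does not commit to one.
3. **Rounding is a legitimate reading of the protocol.** Protocol Table 6-3 gives no score between 0% and 1%, and protocol section 6.4.2 assigns the calculation to the eCRF. Rounding is one way to apply whole-number bands. That makes the eCRF score defensible as a convention, but does not make its zero equal to absence of signs.
4. **The consequence is limited.** The primary variable is loss of PASI 75 (protocol 9.4.1), secondary endpoints are outside the testing strategy (SAP 1.9.3), and the on-treatment response analysis is descriptive. IGA scores are tabulated by visit, and IGA 0 does not depend on area rounding. All of this stands and limits the weight of the point. The IGA response endpoint, though, combines clear with almost clear, so it does not replace a rate of full clearance.
5. **Changing the main definition now would be worse.** The RW analyses are labelled re-runs (SAP 1.1). Sponsor staff were unblinded after Week 68 (protocol 5.4 and 9.6). Recruitment was complete by Amendment 2 of September 2014, so every subject still on study had passed Week 156 (104 weeks after randomization) before the SAP's first draft of June 2017. This is a good reason to add a table and leave the main display alone.

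**Conclusion.** The point holds in a limited form. The SAP's stated rule counts a subject as fully clear when every region with scored signs has an area below 0.5%, and its own unrounded rule disagrees. For PASI 100 the misclassification runs one way. Because the SAP ties the unrounded calculation to scores only, the discrepancy would not show in the reported response rates.

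The size is unknown. If a fraction f of subjects at a visit meets the condition, the PASI 100 rate at that visit is higher by f. Assuming f between 2% and 10% gives 2 to 10 percentage points, but that restates the assumption and is not an estimate.

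The documents do not support three stronger readings:
- **That rounding inflates the difference from placebo.** Both RW arms were to enter as PASI 75 responders, so near-clear subjects can occur in either, and no figures by arm are given.
- **That PASI results in general are biased upward.** The one-way direction applies to PASI 100 only (step 5).
- **That the primary conclusion is in doubt.** Nothing here shows an effect on loss of PASI 75.

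The verdict assumes that sub-integer percentages were entered and kept, as the SAP's examples and its planned unrounded calculation imply.

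**What to change.** Keep the eCRF-based PASI 100 as the main display, for continuity with the Week 68 and core-study analyses. In SAP sections 1.9.1.1 and 1.9.6, add that:

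- PASI 100, and also PASI 75 and 90, will be derived from the unrounded score and tabulated by visit;
- the RW comparison of each dose with placebo will be repeated for PASI 100 on the unrounded score, as a sensitivity analysis;
- the number of eCRF PASI 100 responders with any recorded area above 0% will be reported by visit and treatment group;
- eCRF PASI 100 will not be described as full clearance without that qualification.

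The rounding sentence should also say nearest integer, to agree with its own examples.

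The cost is small: SAP wording, an added derived flag and supplementary tables, using a score that is already to be calculated. The downside is a second full-clearance rate, possibly slightly lower, to be explained beside the main one.
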